4.17.11 Immunogenicity

Immunogenicity analyses will be performed on the Immunogenicity Analysis Set. Three immunogenicity data sets will be analyzed for the study: Anti-Drug Antibodies (ADA) to the transgenic product (REP1), neutralizing timrepigene emparvovec antibodies (Nabs) and ELISpot.

In the ELISpot assay, a subject will be tested using 4 different analytes peptide pools (REP1 Pool 1, REP1 Pool 2, REP2 Pool 3, AAV2) at each visit. All 4 pools together are used to evaluate the immune response to the whole therapeutic product, BIIB111, in which, the 3 REP1 pools are used to evaluate the immune response to the therapeutic gene product, and the AAV2 pool is used to evaluate the immune response to the AAV vector. A subject will be determined to have a positive result to the overall treatment with BIIB111 if any of the 4 analytes is positive. A subject will be determined to have a positive result with respect to the REP1 if any of the 3 REP1 result is positive. A subject will be determined to have a positive result with respect to the AAV2 if the AAV2 analyte is positive.

Samples with a numeric titer are considered as positive for ADA or Nabs respectively. For ELISpot, only samples which have spot counts (presented as SFU=spots per 1 mio cells) 3-fold of control (which is SFU of untreated cells) will present as positive.

All the immunogenicity analyses specified in this section will be performed by assays (ADA, Nabs, ELISpot).

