4.17.11.3 Assay Treatment-emergent Analysis by Visit

The number and percentage of subjects with a positive result will be further tabulated by treatment-emergent status (see definition below, treatment-emergent and non-treat-emergent positive) by, visit, period, surgery windows, and surgery windows combined.

A treatment-emergent positive result is defined as follows for ADA and Nabs:

- A post-baseline result that is positive when the baseline result is negative.
- A post-baseline result that has a titer greater than or equal to 4 times the baseline titer when the baseline result is positive, while titer values are available at both baseline and post-baseline visits.

For ELISpot, the treatment-emergent positive for each analyte is defined as a post-baseline result that is positive when the baseline result is negative. If any of the 3 REP1 analytes is treatment-emergent positive, it is a treatment-emergent positive for REP1. The treatment-emergent positive for AAV2 is defined as a post-baseline result that is positive when the

baseline result is negative for the AAV2 analyte. If either REP1 or AAV2 is treatment-emergent positive, it is a treatment-emergent positive for the overall treatment of BIIB111. The treatment-emergent analysis for ELISpot will be summarized for the overall treatment of BIIB111 as well as with respect to either REP1 or AAV2.

If either the valid baseline samples (see definition above, prior to surgery or Day 1) or valid post-baseline samples at a particular visit are not available, the subject will be assigned as missing for treatment-emergent status at that particular visit and excluded from the treatment-emergent assessment. The remaining available valid baseline samples and post-baseline assessments will be tabulated and contribute to the positive/negative overtime summary mentioned in 14.15.11.2. Invalid sample results include but are not limited to “Quantity Not Sufficient”, “No Results”, etc and will be deemed missing.

For analyses on treatment-emergent immunogenicity, period 1 baseline will be used to derive the change from baseline for data of period 1 visits (before 2nd eye injection) and period 2 baseline will be used to derive the change from baseline for data of period 2 visits (post 2nd eye injection).

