4.17.11.4 Relationship Between Immunogenicity Assay and Safety

The relationship between the immunogenicity assays (ADA, Nab and ELISpot) and selected adverse events will be assessed. These adverse events include ocular inflammation-related adverse events, visual acuity reduced-related adverse events and hypersensitivity-related adverse events. The number and percentage of post-treatment (treatment-emergent) ocular inflammation-related adverse events, visual acuity reduced-related adverse events and hypersensitivity-related adverse events (based on the adverse event data), as well as the number and percentage of eyes with a decrease from baseline of ≥ 15 letters in BCVA at Month 12 (based on the visual acuity assessment data) will be summarized by (1) subjects with negative assay at period 1 baseline; and (2) subjects with positive assay at period 1 baseline; and (3) subjects with at least one treatment-emergent positive assay at any visit during the study; and (4) subjects with no treatment-emergent positive assay during the study. In (3) and (4), to determine the treatment-emergent positivity, the period 1 baseline will be used to calculate the change from baseline for data in period 1 and period 2 baseline will be used to calculate the change from baseline for data in period 2.

The analyses will be conducted by eye, by period and surgery window. It will be repeated by AE severity (mild, moderate and severe) and by AE time to onset (≤ 30 days and > 30 days post-surgery). If an AE has more than one occurrence with an onset ≤ 30 days and another > 30 days, the AE will be reported in both ≤ 30 days and > 30 days' time to onset categories.

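### The SAP's ELISpot positivity rule is a bare 3-fold ratio to control, with no minimum count or zero-control rule, so a low background can turn noise into treatment-emergent responses

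*SAP*

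**What the plan says.** SAP 4.17.11 gives one criterion for an ELISpot positive, a ratio of spot counts: "3-fold of control (which is SFU of untreated cells) will present as positive". It does not say whether this means at least three times or more than three times. Neither document states a minimum SFU, a minimum difference over control, a replicate-well rule, the treatment of a zero control or a validated cut-point.

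Three further rules build on that call:

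- **Across pools (4.17.11).** Each subject is tested against three REP1 pools and one AAV2 pool. "A subject will be determined to have a positive result to the overall treatment with BIIB111 if any of the 4 analytes is positive".
- **Treatment-emergent status (4.17.11.3).** The test is made pool by pool: "For ELISpot, the treatment-emergent positive for each analyte is defined as a post-baseline result that is positive when the baseline result is negative". One emergent pool out of the three is then enough for REP1, and REP1 or AAV2 alone is enough for the product as a whole. For ADA and Nab, a subject who is positive at baseline needs a 4-fold titre rise. ELISpot has no magnitude requirement.
- **Across visits (4.17.11.4).** One group in the comparison with adverse events and vision loss is "subjects with at least one treatment-emergent positive assay at any visit during the study".

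The schedule of procedures (Protocol Table 1) has seven post-dose immunogenicity samples per period: Visits 2 and 4 to 9. Protocol 11.4.2 says only a selection of samples will be analysed and does not say how many. SAP 3.6 justifies the sample size by the immunological profile, which it calls the key concern of re-administration.

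**The concern.** A ratio to a small count is unstable. With a control of one spot, three spots in a pool make a positive; with no spots in the control, the 3-fold ratio is undefined. The rule is therefore least reliable when the assay is cleanest. A subject with no T-cell response has four pools per visit and several visits at which one chance excess is enough.

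Two outputs are exposed. The treatment-emergent T-cell rate could be inflated. In the ELISpot version of the 4.17.11.4 comparison, non-responders could be moved into the treatment-emergent group, which would dilute any real association with inflammation or loss of acuity. In a study of about 60 subjects there is little room for that.

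**Working it through.** The plan states no false-positive rate or cut-point performance for ELISpot, so there is no figure to reproduce. The calculation below is an illustration for a true non-responder.

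**Inputs from the documents**
- 3-fold ratio to untreated cells; four pools, any one sufficient (SAP 4.17.11).
- Treatment-emergent means a pool negative at baseline and positive afterwards (SAP 4.17.11.3); one such result at any visit is enough (SAP 4.17.11.4).
- Up to seven post-dose samples per period (Protocol Table 1), of which a selection is assayed (Protocol 11.4.2). Seven and two assayed visits are used as the range.

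**Assumed, because the documents do not say**
- Poisson counts with the same mean in control and pools.
- 0.6 million cells per condition, so mean raw count λ = 0.6 × background SFU per million. Backgrounds of 5, 10, 25 and 50 SFU give λ = 3, 6, 15 and 30.
- The four pools share one control at each visit.
- A pool is positive if its count is at least three times control and at least one spot.

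**Formulas**
- Given control count C, a pool is positive with probability q(C) = P(X ≥ max(3C, 1)), X ~ Poisson(λ).
- Probability that k given pools are all negative at a visit: E(k) = Σ_C P(C) × (1 − q(C))^k.
- Probability that exactly k of four pools are negative at baseline: w(k) = Σ_C P(C) × [4 choose k] × (1 − q(C))^k × q(C)^(4−k).
- Treatment-emergent at least once in V visits: 1 − Σ_k w(k) × E(k)^V.

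**Worked case: 5 SFU, λ = 3, V = 7**
- q(0) = 0.950, q(1) = 0.577, q(2) = 0.084, q(3) = 0.004. One pool is falsely positive with probability 0.153; at least one of four, 1 − E(4) = 0.264.
- E(1) to E(4) = 0.8469, 0.7900, 0.7578, 0.7359; w(0) to w(4) = 0.0571, 0.0575, 0.0620, 0.0874, 0.7359.
- Σ w(k) × E(k)^7 = 0.0571 + 0.0180 + 0.0119 + 0.0125 + 0.0860 = 0.186, so the probability is 0.814.

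**Results for a non-responder, one period**

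| Background (SFU per million) | Any of 4 pools positive at one visit | Treatment-emergent, 7 visits | Treatment-emergent, 2 visits |
|---|---|---|---|
| 5 | 26% | 81% | 41% |
| 10 | 11% | 55% | 21% |
| 25 | 1.1% | 7.5% | 2% |
| 50 | 0.02% | 0.2% | <0.1% |

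If both periods are fully sampled, each with its own baseline, the chance over the study is 1 − (1 − p)². At 5 and 10 SFU that is 97% and 80% with seven visits per period, and 66% and 37% with two. The AAV2 pool alone, at 5 SFU with seven visits, gives 58% in one period.

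**Effect of a minimum count.** Add a floor of 50 SFU (illustrative). With 0.6 million cells it equals 30 raw spots, and the seven-visit rate is at most 0.2% at all four backgrounds. With 0.2 million cells it equals only 10 raw spots, and the rate is still about 23% at 25 SFU and 24% at 50 SFU. The floor has to be set with the cell number in view.

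**The case against.** **The percentages rest on inputs that the documents lack.** This stands. Across the assumed backgrounds the one-period result runs from 81% to under 0.1%, and nothing shows where this assay lies. A reader might infer that most non-responders will be treatment-emergent, or that the ELISpot rate merely measures background. The documents do not support that: in one period, more than half arises only at the two lowest backgrounds with all seven visits assayed, and Protocol 11.4.2 leaves the number of assayed visits open.

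**The SAP wording may be a necessary condition rather than the whole call rule.** Results come from a central laboratory as an external data set (Protocol 15.2), and the laboratory may apply a floor of its own. That is possible. But the SAP neither states nor cites one, although for the adverse-event term lists it does point to an outside document (4.17.10). For the same reason, one should not infer that a zero control makes every sample positive. A ratio to zero is undefined, and the fault is that the SAP leaves it so.

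**The damage is contained.** Much of this stands. Immunogenicity analyses are run separately by assay, so the ADA and Nab versions of 4.17.11.4 are untouched. REP1 and AAV2 are also reported separately, although each remains exposed. There is no formal comparison (SAP 4.2), no decision or stopping rule in the documents uses ELISpot status, and SFU values are listed by subject (4.17.11.5), so low-count positives could be seen. SAP 4.17.11.3 already deems invalid results missing.

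These points lower the severity. They do not supply the missing criterion.

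**Conclusion.** The gap is in the text: the ELISpot call is a ratio with no minimum count, no zero-control rule and no cited cut-point. At low background it can label noise as a response, and the pool, baseline-to-post and visit rules compound the error. The size is conditional. It is large at 5 to 10 SFU under the stated assumptions and negligible near 50 SFU with 0.6 million cells per condition. The direction is an inflated treatment-emergent T-cell rate and a diluted ELISpot-safety association.

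It would go too far to conclude that the immunogenicity-safety analysis as a whole is noise, since two of its three assays are unaffected. It would also go too far to conclude that any fixed floor cures the problem, since the result depends on cell number. With purely descriptive analyses this should be fixed; it does not invalidate the plan.

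**What to change.** In SAP 4.17.11, call a pool positive only if its SFU is at least three times control and also exceeds a fixed minimum SFU, or a minimum difference over control. Take that value from the assay validation and set it with the number of cells plated in mind. State how a zero control is handled. In 4.17.11.3, name failure of the control-well validity limit as one of the invalid results already deemed missing. Apply all of this before the any-of-four rule, and fix it before results are reviewed, because a cut-off chosen afterwards in an open-label study would be data-driven. If the laboratory already applies such a rule, state or cite it.

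The cost is a short SAP amendment, provided that the validation limits exist, and no new assay work. SFU values are already to be listed (4.17.11.5), but confirm that control-well SFU is included in the data transfer. The drawback is that a weak true response below the minimum would be called negative.

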4.17.11.1 Baseline Definition

As the second eye treatment in Period 2 in GEMINI may potentially increase the risk of a subject developing an immune response against the therapeutic product, BIIB111, we define two different types of baselines to evaluate the treatment emergent immune response, anchored to the time when the first eye was treated, and when the second eye was treated, respectively. The definition is as below.

Period 1 baseline is defined as the last available value prior to surgery of the first eye. For subjects without any assessments prior to surgery of the first eye, Day 1 sample will be used as baseline. If neither assessment prior to surgery of the first eye nor Day 1 sample are available, the period 1 baseline is set missing.

Period 2 baseline is defined as the last available value within 10 weeks prior to the surgery of the second eye. For subjects without any assessments within 10 weeks prior to surgery of the second eye, Day 1 sample post-second eye surgery will be used as baseline for period 2. If neither assessment prior to surgery of the second eye nor Day 1 sample are available, the period 2 baseline is set missing.

Note that the immunogenicity data is collected as one record per subject per visit.

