The interval between SE1 and SE2 treatment is expected to vary among subjects from weeks to many months. While the interval will be decided on a case-by-case basis, an effort will be made to schedule varying treatment intervals in order to better characterise the immunological and safety profile of sequential treatment administration. Thus, approximately 20 subjects each will be treated with a short- (<6 month), medium- (6-12 months), or long- (>12 month) surgery window between treatment of the first and second

eye. Because the timing of the second surgery visit (Period 2, Visit 1) will vary among subjects, the duration of study Period 1 will also be variable.

The post-operative outcome and visual function of SE1 will inform the scheduling of Period 2. Signs of post-operative inflammation or other post-operative sequelae, as judged by the Investigator, should be resolved in SE1 for the subject to continue to Period 2. After comprehensive evaluation of all safety assessments and visual functional tests of SE1 and SE2, the Investigator will determine the eligibility of the subject and decide the appropriate time to schedule SE2, Visit 1.

All baseline ophthalmic assessments must be conducted within 10 weeks prior to SE2 surgery (Period 2, Visit 1). If these assessments are not available within the required timeframe, a Baseline Visit must be added to collect current baseline data on SE2. Study eye selection and eligibility for surgery will then be confirmed collectively by the Patient Eligibility Review Committee, which includes the Investigator, a consulting surgeon, and the Sponsor (see the Patient Eligibility Review Plan). If, at that time, BCVA in SE2 is <34 ETDRS letters, surgery may be performed when, in the opinion of the Patient Eligibility Review Committee: 1) the subject is found eligible by all other inclusion and exclusion criteria, and 2) the subject is considered an appropriate candidate who has potentially modifiable disease.

At Period 2, Visit 1 (Day 0, Injection Day Visit for SE2) subjects will undergo a vitrectomy with retinal detachment and sub-retinal injection of AAV2-REP1 in the contralateral, untreated eye (SE2). Post-treatment, subjects will no longer follow the Period 1 visit schedule, but will instead attend Period 2, Visits 2-9 according to the Schedule of Study Procedures. Ophthalmic assessments scheduled for Period 2, Visits 2-9 will be performed on both eyes.

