10.1.1 Baseline Visit, Period 2 (<10 Weeks from Visit 1, Period 2 [SE2])

The following baseline assessments for Period 2 must be performed within 10 weeks prior to surgery for SE2 (Visit 1, Period 2). If the assessments have not been performed within a regularly scheduled visit within this window, an additional visit is required.

- Vital signs
- Weight
- Vector shedding sampling – blood, tears (both eyes), urine, saliva
- Immunogenicity sampling
- BCVA
- Microperimetry

- Full ophthalmic examination, including IOP, a slit-lamp examination, lens opacity, and dilated fundus examination
- SD-OCT
- AF
- 7-field colour fundus photography (including stereo photographs for fields 1, 2, and 3)
- AE and SAE monitoring
- Concomitant medication, procedures and treatment review

Eligibility for SE2 surgery will then be confirmed collectively by the Patient Eligibility Review Committee, which includes the Investigator, a consulting surgeon, and the Sponsor (see the Patient Eligibility Review Plan).

If BCVA in SE2 is <34 ETDRS letters, surgery may be performed when, in the opinion of the Patient Eligibility Review Committee:

1. the subject is found eligible by all other inclusion and exclusion criteria, and
2. the subject is considered an appropriate candidate who has potentially modifiable disease.

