13 STATISTICAL CONSIDERATIONS

13.1 Sample Size

Approximately 60 subjects are planned to be enrolled in the study. A total of 120 treated eyes is considered sufficient to characterise the immunological profile of bilateral AAV2-REP1 administration, which is the key concern of gene therapy re-administration.

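### A Period 2 immunogenicity baseline up to 10 weeks old lets first-dose responses be tabulated as emergent after the second eye, most likely in the short surgery window

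*SAP*

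**What the plan says.** SAP 4.17.11.1 defines one immunogenicity baseline per surgery, so that an emergent response can be tied to the treatment of each eye. For the second eye: "Period 2 baseline is defined as the last available value within 10 weeks prior to the surgery of the second eye". Only if that window is empty is there a fallback: "Day 1 sample post-second eye surgery will be used as baseline for period 2".

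SAP 4.17.11.3 applies this baseline to everything after the second injection: "period 2 baseline will be used to derive the change from baseline for data of period 2 visits (post 2nd eye injection"). For ADA and Nabs there are two routes to emergence: "A post-baseline result that is positive when the baseline result is negative", or "A post-baseline result that has a titer greater than or equal to 4 times the baseline titer when the baseline result is positive". ELISpot has only the first route. Results are tabulated by visit, period and surgery window.

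The protocol sets the same age limit in 10.1.1: "The following baseline assessments for Period 2 must be performed within 10 weeks prior to surgery for SE2 (Visit 1, Period 2"). Immunogenicity sampling is on that list. A regular visit inside the window can serve; otherwise an extra visit is added. Protocol 10.2 and Table 1 show no immunogenicity sample at Visit 1 (Day 0); the next one is at Visit 2 (Day 1). Protocol 11.4.2 says that selected samples, not all of them, will be assayed.

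On purpose, Protocol 13.1 says of the immunological profile: "which is the key concern of gene therapy re-administration". Protocol 7.1 varies the interval to characterise it: "approximately 20 subjects each will be treated with a short- (<6 month), medium- (6-12 months), or long- (>12 month) surgery window".

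**The concern.** The Period 2 baseline is meant to mark the state just before the second dose. With no sample on the day of surgery, it marks the state at some earlier point, up to 70 days before. Whatever the first dose does between that sample and SE2 surgery is read as a Period 2 event. No rule in the SAP prevents this, flags it or tests sensitivity to it.

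What is at stake is the reading of the Period 2 emergence tables by surgery window. A response to the first dose is more likely to be still developing when SE2 follows SE1 by weeks than when it follows by more than a year. Mixed-in first-dose responses would therefore tend to raise the short-window figure, and could resemble the interval effect that the three windows are there to describe.

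**Working it through.** The plan gives no figure to reproduce here. The check is of the schedule, followed by an illustration under stated assumptions.

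**Inputs**
- Period 1 immunogenicity samples: Days 1, 7 and 14, and Months 1, 3, 6 and 12 (Protocol Table 1). Target days for the months: 30, 91, 182 and 365 (SAP Table 2). None on Day 0 or Day 3.
- Age limit: 10 weeks = 70 days (SAP 4.17.11.1, Protocol 10.1.1). SAP 3.1 and SAP Table 3 still carry 3 months and 12 weeks for the Period 2 baseline visit; 70 days is used here because it is the limit in the immunogenicity definition.

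**Age of the last scheduled sample.** For SE2 surgery on day T after SE1, age = T − (latest sample day before T), accepted if ≤ 70.

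| T | Latest sample | Age (days) |
|---|---|---|
| 21 | Day 14 | 7 |
| 30 | Day 14 | 16 |
| 60 | Day 30 | 30 |
| 91 (Month 3 slot) | Day 30 | 61 (8.7 weeks) |
| 150 | Day 91 | 59 |
| 161 | Day 91 | 70 |
| 162 to 182 | Day 91 | over 70, not accepted |

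The Month 3 row matters because Protocol 10.1 asks sites to place SE2 surgery at a planned Period 1 visit where possible.

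Over T = 14 to 182 (169 days), 169 − 21 = 148 days have a qualifying scheduled sample, with median age 29 days. It is more than 28 days old for T = 59 to 91 (33 days) and T = 120 to 161 (42 days): 33 + 42 = 75, and 75/169 = 44%.

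**Example.** A subject is ADA-negative at SE1 Month 1 (Day 30), converts on Day 60 and has SE2 surgery on Day 90. If no fresher sample exists, his baseline is negative and 60 days old. He is positive on Period 2 Day 1 and is tabulated as Period 2 treatment-emergent one day after the second injection.

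**Illustration.** The following assumptions are not in the documents. Time to first-dose conversion is lognormal with log-SD 0.6. T is uniform within each window (21–182, 183–365 and 366–548 days). The last scheduled sample is the baseline if it is within 70 days; otherwise an extra visit falls 14 or 70 days before surgery. The table gives the share of first-dose conversions that fall between the baseline sample and SE2 surgery.

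| Median time to conversion | Short | Medium | Long |
|---|---|---|---|
| 14 days | 5% | 0% | 0% |
| 30 days | 16% | 0% | 0% |
| 60 days | 20–22% | about 1% | 0% |
| 90 days | 18–21% | 2–4% | 0.3% or less |

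The denominator is first-dose converters, not subjects. The table also assumes no extra visit when a scheduled sample qualifies, which leans towards older baselines.

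**What a fresh sample cannot remove.** Some first-dose conversions appear only after SE2 surgery and count as Period 2 whatever the baseline. In the short window, all first-dose conversions labelled Period 2 would fall, with a pre-dose Day 0 sample, from 7% to 2%, 26% to 10%, 50–52% to 31%, and 66–70% to 49% for the four medians in turn.

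The error is not all one way. A rise of 2-fold before the Period 2 baseline and 2-fold after it is 2 × 2 = 4-fold in all, yet is emergent in neither period.

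**The case against.** The best defence is that the Month 1 sample will often not be the baseline. The Protocol 10.1.1 list includes weight, vital signs and 7-field fundus photography, and none of these is scheduled at Months 1 or 3. Unless they are added to a regular visit, or Screening is itself recent enough, a separate baseline visit follows and brings its own immunogenicity sample. This stands, and it lowers the exposure. It does not remove it: Protocol Table 1 footnote b accepts a regular visit within 10 weeks, and a separate visit may be up to 10 weeks old too.

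Second, the tables are by visit, and SAP 4.17.11.5 lists individual status and titre, so a subject like the one in the example would appear in the Period 2 Day 1 row. That is true for Day 1. If he stays positive he is also counted at Day 7 and later, where no row separates him.

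Third, everything is descriptive. That is also true, but these tables are the immunogenicity result, and a descriptive count can still be credited to the wrong dose.

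A reader might infer that the SAP contradicts itself, since Period 2 Day 1 serves as baseline for some subjects and as a post-baseline visit for others. That goes too far. Day 1 is a fallback for a missing sample, used the same way in Period 1, and preferring a pre-dose sample does not claim that the two are equivalent. What the fallback does show is that the SAP is willing to read a Day 1 result as a baseline, which is enough to justify a flag.

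A reader might also infer that group (3) of SAP 4.17.11.4 is inflated. It is not, in this case. That group holds subjects with an emergent positive at any visit in the study, and a subject who converts after the first dose belongs there. Moving everyone to a Day 1 baseline would do harm: with negative Period 1 visits and a positive Period 2 baseline, he could drop into group (4).

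**Conclusion.** The mechanism is documented and needs no assumption: a baseline up to 10 weeks old, no sample on the day of surgery, and all Period 2 results judged against that baseline alone. A first-dose conversion or 4-fold rise in the gap is tabulated as emergent in Period 2. The point should be addressed in the SAP.

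The size is unknown. The documents give no response kinetics, so the percentages above are illustrations only. That the problem is most likely in the short window held under every median tried (14 to 90 days), but it rests on first-dose responses arising mainly in the first months.

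Two stronger readings are tempting. One is that the whole short window, about 20 subjects, is misclassified. That figure is only a ceiling: for surgery by about Day 30 the scheduled samples are at most 16 days old, a separate visit may supply a later one, and only subjects who cross the threshold in the gap count. The other is that a higher short-window rate would be an artefact. The documents do not support that either; they show only that the tables as planned could not tell the two explanations apart.

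**What to change.** Keep the main baseline rule in SAP 4.17.11.1. In SAP 4.17.11.3:

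- Flag subjects who, on Period 2 Day 1, are already newly positive or at least 4-fold higher than their pre-surgery baseline. Show them by surgery window in a separate row, labelled as emerged by Period 2 Day 1 and not attributable to the second dose.
- Add a supportive Period 2 treatment-emergent table from Day 7 onward, using the Period 2 Day 1 result as baseline where it was assayed. It should be supportive only, because a higher baseline titre makes a 4-fold rise harder to reach.
- State that first-dose responses first appearing after SE2 surgery cannot be separated from second-dose responses.

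Leave groups (3) and (4) of SAP 4.17.11.4 as they are, so that flagged subjects stay in group (3).

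The cost is SAP wording, derivation code and one extra table. The Day 1 sample is already scheduled, but it must be among those selected for assay. The label and the supportive table take it that the second dose produces no response within one day; a true response that fast would be missed.
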